**Figure 7-1 VX21-548-103 Study Design**

N: number of subjects

a At the end of the Treatment Period (Week 12), subjects will taper off capsule (pregabalin reference or matched placebo) study drug for 7 days.

A total of approximately 175 subjects will be randomized 2:2:1:2 to 4 treatment arms: VX-548 (high, mid, or low dose) or pregabalin (reference arm) (Table 7-1). Randomization will be stratified by sex (female and male) and body mass index ( $\geq 30$  and  $< 30$  kg/m^2). To maintain the blind, all subjects will receive the same number of tablets once daily (qd) in the morning and the same number of capsules 3 times per day in a double-dummy design. After the Treatment Period, subjects will taper off capsule (pregabalin reference or matched placebo) study drug for 7 days (4 days of dosing every 12 hours, then 3 days of dosing qd), and the Safety Follow-up Visit will occur an additional 7 ( $\pm 2$ ) days later.

**Table 7-1      VX21-548-103 Treatment Arms**

Treatment	Active Dose	Number of Subjects (Planned)
VX-548 (high dose)	69 mg qd	50
VX-548 (mid dose)	46 mg qd	50
VX-548 (low dose)	23 mg qd	25
Pregabalin	100 mg tid	50

qd: once daily; tid: 3 times per day

Note: To maintain the blind, all subjects will receive the same number of tablets and the same number of capsules at the same respective frequency (i.e., qd for tablets and tid for capsules during the Treatment Period) in a double-dummy design.

Subjects will stop taking pain medications (including pregabalin, if applicable), except acetaminophen (500 mg), for at least 14 days before the first dose of study drug. Acetaminophen will be permitted as a pain rescue medication as needed (prn) throughout the study. Subjects will be permitted to take 500 mg every 4 to 6 hours prn, up to a maximum of 2500 mg in any 24-hour period. Subjects will record rescue medication use, and their current pain score on the NPRS immediately before each administration of rescue medication. Rescue medication usage will only be documented up to treatment discontinuation.

## **7.2              Sample Size and Power**

The sample size is based on the primary analysis of the primary endpoint. With 37 evaluable subjects in the VX-548 high or mid dose group and 18 evaluable subjects in the VX-548 low dose group, there is more than 90% power in any VX-548 dose group to detect a mean change from baseline of 3 with a single group *t*-test at the 2-sided 0.05 significance level, assuming the SD is 2.3. With an evaluable sample size of 37, a 2-sided 95% CI for the mean change from baseline in the high or mid dose group will extend 0.77 on either side of the observed mean, assuming the CI is based on the *t*-statistic and the observed SD is 2.3. Under the same assumptions and an evaluable sample size of 18, a 2-sided 95% CI for the mean change from baseline in the low dose group will extend 1.14 on either side of the observed mean. To account for a 25% dropout rate, 50 subjects each will be enrolled in the VX-548 high dose, VX-548 mid dose, and the pregabalin groups; 25 subjects will be enrolled in the VX-548 low dose group. The total sample size is approximately 175 subjects.

The study is not powered for comparison between the VX-548 doses and the pregabalin reference arm.

## **7.3              Randomization**

Refer to Section 9.2 of the CSP for details.

## **7.4 Blinding and Unblinding**

Refer to Section 10.7 of the CSP for details.

# **8 ANALYSIS SETS**

## **8.1 All Subjects Set**

The **All Subjects Set** is defined as all subjects who have been randomized or have received at least 1 dose of study drug. This analysis set will be used in subject listings and disposition summary table, unless otherwise specified.

## **8.2 Full Analysis Set**

The **Full Analysis Set (FAS)** is defined as all randomized subjects who have received at least 1 dose of study drug. The FAS is to be used to summarize subject demographics and baseline characteristics. It is also to be used in all efficacy analyses, in which subjects will be analyzed according to their randomized treatment group.

## **8.3 Safety Set**

The **Safety Set** is defined as all subjects who have received at least 1 dose of study drug. The Safety Set is to be used for all safety analyses in which subjects will be analyzed according to the treatment they received.

# **9 STATISTICAL ANALYSIS**

## **9.1 General Considerations**

The Schedule of Assessments is provided in Section 3 of the CSP. The precision standards for reporting variables are provided in an internal Biometrics document that specifies the programming rules including the precision for derived variables.

All individual subject data for subjects who were randomized or received at least 1 dose of study drug will be presented in individual subject data listings.

**Continuous variables** will be summarized using the following descriptive summary statistics: the number of subjects (n), mean, standard deviation (SD), median, minimum value (min), and maximum value (max), unless otherwise specified.

**Categorical variables** will be summarized using counts and percentages.

**Baseline value:** The baseline for the weekly average of NPRS and DSIS will be defined as average of the non-missing scores from Day -7 to Day -1. For the weekly average of NPRS, baseline values will be calculated if there are at least 4 non-missing scores. For weekly average of DSIS, baseline values will be calculated if there are at least 3 non-missing scores. For ECGs, the baseline values will be defined as the most recent average of non-missing triplicate measurements collected before the first dose of the study drug. For all other variables, baseline values will be defined as the most recent non-missing measurement collected before the first dose of study drug, unless otherwise specified.

**Change (absolute change) from baseline** will be calculated as post-baseline value – baseline value.

**Treatment-emergent (TE) Period** will include the time period from the date of the first dose of study drug to either (1) the Safety Follow-up Visit, (2) the ETT Visit if it replaces the Safety Follow-up Visit, or (3) 14 days after the last dose for subjects who do not have a Safety Follow-up Visit or equivalent.

**Unscheduled visits:** Unscheduled visit measurements will be included in the analysis as follows:

- In scheduled visit windows per specified visit windowing rules
- In the derivation of baseline
- In the derivation of maximum and minimum values during the TE period, and maximum and minimum change from baseline values during the TE period for safety analyses
- In individual subject data listings as appropriate

**Visit windowing rules:** The analysis visit windows for protocol-defined visits are provided in [Appendix A](#).

**Incomplete/missing data:** Details on how to handle missing data are described in subsequent sections when applicable.

**Outliers:** No formal statistical analyses will be performed to detect and/or remedy the presence of statistical outliers.

**Multiplicity:** There is no multiplicity adjustment for this Phase 2 study.

## **9.2 Background Characteristics**

### **9.2.1 Subject Disposition**

The disposition summary will be provided by treatment group and overall.

The number of subjects in the following categories will be summarized:

- All Subjects Set
- Randomized
- Full Analysis Set (FAS)
- Safety Set
- Randomized but not dosed

The number and percentage (based on the FAS) of subjects in each of the following disposition categories will be summarized:

- Completed treatment

- Prematurely discontinued treatment and the reason for discontinuation from treatment
- Completed study
- Prematurely discontinued the study and the reason for discontinuation from study
- Complete taper
- Did not complete taper

A disposition listing and a randomization listing of subjects will be provided.

### **9.2.2 Demographics and Baseline Characteristics**

Demographics and baseline characteristics will be summarized based on the FAS by treatment group and overall.

Demographic data will include the following:

- Age at screening (in years)
- Age at screening category ( $\geq 18$  to  $< 65$ ,  $\geq 65$ )
- Sex (male, female)
- Ethnicity (Hispanic or Latino, not Hispanic or Latino, and not collected per local regulations)
- Race (White, Black or African American, Asian, American Indian or Alaska Native, Native Hawaiian or Other Pacific Islander, not collected per local regulations, Other and Multiracial [if 2 or more races reported from a subject])

Baseline characteristics will include the following:

- Weight (kg)
- Height (cm)
- BMI ( $\text{kg}/\text{m}^2$ )
- BMI category ( $\geq 30$  and  $< 30 \text{ kg}/\text{m}^2$ )
- Baseline HbA1c (%)
- Baseline HbA1c category ( $< 7$  and  $\geq 7\%$ )
- Baseline weekly average of NPRS
- Baseline weekly average of NPRS category ( $< 8$ ,  $\geq 8$ )
- Baseline weekly average of DSIS
- Baseline NPSI total score
- Baseline SF-36 physical component summary score
- Baseline SF-36 mental component summary score
- Baseline SF-MPQ-2 total score

- Baseline BDI-2 total score

The scoring of NPSI, SF-36, SF-MPQ-2 and BDI-2 are included in Appendix B.

In addition to demographic data and baseline characteristics, data listings will also be provided for:

- Informed consent
- Inclusion/exclusion criteria violation for subjects with any such violations

### **9.2.3 Medical History**

Medical history will be coded using the Medical Dictionary for Regulatory Activities (MedDRA). Medical history will be summarized descriptively based on the FAS by MedDRA system organ class (SOC) and preferred term (PT). This summary will be provided by treatment group and overall. The corresponding data listing will also be provided.

### **9.2.4 Prior and Concomitant Medications**

Medications will be coded using the World Health Organization Drug Dictionary and categorized as the following for the purposes of analysis:

**Prior medication:** Medication that started before the first dose of study drug, regardless of when dosing of the medication ended

**Concomitant medication:** Medication continued or newly received after the date and time of the first dose of study drug through the end of the TE Period

A given medication may be classified as a prior medication, a concomitant medication, or both a prior and a concomitant medication.

If a medication start date/time is on or after the first dose of study drug, then the medication will be classified as a concomitant medication regardless of whether the medication end date/time is missing. If a medication end date/time is before the first dose of study drug, then the medication will be classified as a prior medication regardless of whether the medication start date/time is missing.

Note that a medication that started before the first dose of study drug and continued after the first dose will be classified as a prior medication and separately as a concomitant medication. If a medication has a missing or partially missing start or end date/time and it cannot be determined whether it was taken before the first dose of study drug or concomitantly, it will be classified as a prior and a concomitant medication.

Details for imputing missing or partial start/end date and time of medication are described in Appendix C.

Prior and concomitant medications will be summarized based on the FAS by Preferred Name and listed. This summary will be provided by treatment group and overall. Prior pain medications will be included in the summary of prior medications and will also be summarized and listed separately. Concomitant analgesic medications other than rescue medication will be included in the summary of concomitant medications and will also be summarized and listed separately. Rescue medication, as collected in the e-diary, will not be

included in the summary of concomitant medications and will be summarized separately. Prior and concomitant non-pharmacological treatments or procedures will be listed.

### **9.2.5 Study Drug Exposure and Study Drug Compliance**

Study drug exposure and study drug compliance will be summarized based on data collected in eCRF.

Duration of study drug exposure (in days) will be calculated as (last date of dosing in the treatment period – first date of dosing +1). Duration of study drug exposure in weeks will be summarized by treatment group (based on FAS) using descriptive summary statistics and by frequency count and percentages for the following categories:  $\leq 1$  week,  $>1$  and  $\leq 2$  weeks,  $>2$  and  $\leq 3$  weeks, ...,  $>11$  weeks and  $\leq 12$  weeks and  $>12$  weeks.

Study drug compliance rate will be calculated as  $100 \times [1 - (\text{total number of days of study drug interruption between the last dose date in the treatment period and first dose date}) / (\text{duration of study drug exposure in days})]$ . Study drug compliance rate will be summarized descriptively (based on FAS) by treatment group and overall and into the categories of  $<80\%$ , and  $\geq 80\%$ .

### **9.2.6 Important Protocol Deviations**

An important protocol deviation (IPD) is a deviation that may significantly affect the completeness, accuracy, or reliability of the study data or that may significantly affect a subject's rights, safety, or well-being. IPD rules will be developed and finalized before database lock. IPDs will be identified by the PD review team according to the protocol deviation plan.

IPDs will be summarized descriptively based on FAS by treatment group and overall, as well as presented in an individual data listing.

## **9.3 Efficacy Analysis**

All efficacy analyses described in this section will be based on the FAS. Subjects will be analyzed according to their randomized treatment assignment.

### **9.3.1 Analysis of Primary Endpoint**

#### **9.3.1.1 Definition of Primary Estimand**

The primary endpoint is the change from baseline in the weekly average of daily pain intensity on an NPRS at Week 12. The primary estimand is defined as the following:

- Treatment: VX-548 + rescue medication (if used)
- Population: Study population defined by the study inclusion and exclusion criteria
- Variable: change from baseline in the weekly average of daily pain intensity on an NPRS at Week 12

- Handling of intercurrent events:
  - The hypothetical strategy will be used to handle treatment discontinuation, which means that the observed NPRS scores up to treatment discontinuation will be used.
  - The treatment policy strategy will be used to handle rescue medication use, which means that the observed NPRS scores on the days when subjects take rescue medication will be used.
- Population level summary: Variable mean

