9.4 Study Restrictions

Study restrictions are summarized in Table 9-2. A non-exhaustive list of study restrictions will be provided in the Study Reference Manual.

Table 9-2 Study Restrictions

| Restricted | Timing of Restriction | | |
|---|--|--|--|
| Medication/Food/Activity a | Start | Stop | |
| Other investigational drugs or devices | 30 days before first dose of study drug, 5 half-lives before first dose of study drug, or time determined by local requirements (whichever is longer) | Completion of SFU assessments | |
| Any opioid use for chronic (including neuropathic) pain; for acute use, refer to Section 8.2 and Section 11.5.2 | 3 months before Screening Visit 1 | Completion of Week 12 or ETT Visit assessments | |
| Marijuana or marijuana products | 14 days before first dose of study drug | Completion of Week 12 or ETT Visit assessments | |
| Pregabalin (except use of reference study drug) and gabapentin | 14 days before first dose of study drug | Completion of study drug taper (i.e., 7 days after Week 12 or ETT Visit) | |
| Capsaicin patch | 90 days before first dose of study drug | Completion of Week 12 or ETT Visit assessments | |
| Lamotrigine, carbamazepine, oxcarbazepine, phenytoin, topiramate, valproic acid, mexiletine, and topical agents being prescribed for pain control | 14 days before first dose of study drug | Completion of Week 12 or ETT Visit assessments | |

Table 9-2 Study Restrictions

| Restricted | Timing of Restriction | | |
|--|--|---|--|
| Medication/Food/Activity a | Start | Stop | |
| All SNRIs and tricyclic antidepressants | 14 days before first dose of study drug | Completion of Week 12 or ETT Visit assessments | |
| All other treatments for pain, except acetaminophen (500 mg) and study drug (as outlined in Section 9.4.1), including nonpharmaceutical interventions | 14 days before first dose of study drug | Completion of Week 12 or ETT Visit assessments | |
| Oral steroids | 5 half-lives or 2 days (whichever is longer) before first dose of study drug | Until last dose of study drug is taken | |
| Medications, herbal and dietary supplements (including St. John's wort) known to be moderate or strong inducers of CYP3A | 14 days before first dose of study drug | Completion of SFU assessments | |
| Proton Pump Inhibitors | 72 hours before first dose of study drug | Until last dose of study drug is taken | |
| H2 blockers | 12 hours before each morning dose of study drug | 6 hours after each morning dose of study drug | |

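### The primary estimand gives no strategy for prohibited analgesic use on study drug, so those NPRS scores are kept by default and such subjects can count as responders

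*SAP*

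**What the plan says.** **Estimand (SAP 9.3.1.1).** The treatment attribute is study drug plus rescue ("Treatment: VX-548 + rescue medication (if used"). Rescue is acetaminophen (SAP 7.1; protocol 9.4.1). Two intercurrent events are named. Treatment discontinuation takes the hypothetical strategy, meaning that "the observed NPRS scores up to treatment discontinuation will be used". Rescue use takes the treatment policy strategy.

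**Analysis (SAP 9.3.1.2).** Weekly averages use the non-missing scores up to treatment discontinuation, with no other exclusion. The comparison is within each VX-548 group.

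**Secondary endpoints (SAP 9.3.2).** The NPRS responder endpoints use the primary-analysis weekly averages. DSIS follows the same up-to-discontinuation rule. For the NPRS responder and PGIC endpoints, subjects who stop treatment early are non-responders, and completers with a missing Week 12 value are imputed from their last available one.

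**Restrictions (protocol 9.4, Table 9-2, and 9.4.1).** Gabapentin and non-study pregabalin are barred until the end of the taper. SNRIs, tricyclics and other pain treatments are barred to the Week 12 or ETT Visit. Stable cardiovascular aspirin is allowed. The opioid row reads "Any opioid use for chronic (including neuropathic) pain; for acute use, refer to Section 8.2 and Section 11.5.2".

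**Reporting.** SAP 9.2.4 states that "Concomitant analgesic medications other than rescue medication will be included in the summary of concomitant medications", and that they are also summarized and listed separately. Important protocol deviations are summarized and listed (SAP 9.2.6).

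**The concern.** A subject on gabapentin plus VX-548 is not receiving the treatment that the estimand describes, yet the scores count towards it because no strategy says otherwise. The subjects likeliest to add an analgesic are those with too little relief. Without a control arm in the primary comparison, any relief from the added drug appears as change from baseline on VX-548.

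The responder endpoints show the asymmetry most clearly. A subject who stops tablets for lack of relief is a non-responder. One who keeps taking tablets and adds a prohibited analgesic can be a responder. If such use differed between doses it would also blur the dose-ranging picture, though nothing in the documents shows that it would.

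**Working it through.** **1. Does anything else in the visible text remove these scores?**

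- Analysis set: all efficacy analyses use the FAS (SAP 9.3), and no per-protocol set is defined (SAP 8).
- Deviations: summarized and listed, with no data rule (SAP 9.2.6).
- Stopping rules: protocol 9.8 and 9.9 concern serious adverse events. Withdrawal for noncompliance with procedures is discretionary (9.10), and 10.6 concerns study drug dosing.
- Drug testing: the panel in protocol 11.5.2 includes opioids but not gabapentin, SNRIs or tricyclics.

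So retention follows from the general rule plus silence. No sentence states it outright.

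**2. Reproduce the planning figures (SAP 7.2).** Inputs: "With 37 evaluable subjects in the VX-548 high or mid dose group and 18 evaluable subjects in the VX-548 low dose group"; "to detect a mean change from baseline of 3 with a single group" test; "single group *t*-test at the 2-sided 0.05 significance level, assuming the SD is 2.3". Half-width = t(0.975, n−1) × 2.3/√n. Power is from the noncentral t.

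| n | Half-width | Stated | Power at a change of 3 |
|---|---|---|---|
| 37 | 0.767 | 0.77 | >99.99% |
| 18 | 1.144 | 1.14 | 99.94% |

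The planning figures are correct.

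**3. Size of the shift.** Let p be the share of an arm using a prohibited analgesic in Week 12 and r the extra relief in NPRS points. Neither is in the documents; both are assumed. Shift in the arm mean = p × r, a complete-data approximation to the Week 12 LS mean.

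| p | r | Shift | Share of 0.77 | Share of the planned change of 3 |
|---|---|---|---|---|
| 5% | 1 | 0.05 | 6.5% | 1.7% |
| 10% | 1 | 0.10 | 13% | 3.3% |
| 10% | 2 | 0.20 | 26% | 6.7% |
| 15% | 2 | 0.30 | 39% | 10% |

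Against the low dose half-width of 1.14, the largest shift is 0.30/1.14 = 26%.

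**4. Effect on the test.** If the true mean change were 0, a shift of 0.20 would raise the rejection rate from 5% to 8.1% (n = 37) or 6.4% (n = 18). A shift of 0.30 would raise it to 12.1% or 8.2%. If the true change were 2.7 and a 0.30 shift made it look like 3, power without the shift would still be above 99.9% (n = 37) and 99.7% (n = 18). So significance near the planned effect does not depend on these scores.

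**5. Would deleting the scores be better?** Two-timepoint approximation to the MMRM: true mean change −3 and SD 2.3 at both times, assumed correlation 0.7, and the 10% of subjects with least relief switching. Affected Week 12 values are set to missing and the earlier score is used under missing at random.

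| Switching depends on | Estimate after deletion | Estimate keeping scores (r = 1 to 2) |
|---|---|---|
| Earlier recorded score | −3.00 | −3.10 to −3.20 |
| Current lack of relief | about −3.26 | −3.10 to −3.20 |

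In the second row, deletion has the smaller bias only if r exceeds about 0.26/0.10 = 2.6 points. Neither rule is better in every case.

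**6. Precision cost of a deletion analysis.** With n = the whole part of N × (1 − p) and p from 5% to 15%, 37 falls to 35–31 (half-width 0.79–0.84) and 18 falls to 17–15 (1.18–1.27). Power at a change of 3 stays above 99.6%.

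**The case against.** **The SAP 9.2.4 table does not prove that prohibited use is expected.** A reader might infer from the separate analgesic summary that the sponsor foresees such use on treatment. The documents do not support that. The table runs to the end of the treatment-emergent period, normally the Safety Follow-up Visit, so it also captures use after most restrictions end, use after early discontinuation, and possibly aspirin. This stands.

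**Controls exist.** Subjects are asked about medications at every visit (protocol 9.5), can be withdrawn from study drug for noncompliance (9.10), and are drug tested during treatment. Withdrawal would drop later scores. This stands in part: withdrawal is discretionary, and scores between starting the analgesic and stopping study drug remain.

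**Acute opioid use is a weak example.** Protocol 11.5.2 requires negative drug tests to receive study drug. Whether that applies after entry is unclear. The point rests on gabapentin, SNRIs and tricyclics instead.

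**Deletion is not a clean remedy.** This stands. As step 5 shows, it can overstate benefit by more than keeping the scores does. It is therefore not proposed as the primary rule.

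**Redaction.** Material between SAP 9.3.2 and 9.3.4 is redacted, so a relevant sensitivity analysis cannot be ruled out. The visible primary estimand and responder definitions still do not address the event.

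**Conclusion.** The gap is real and modest. A foreseeable intercurrent event has no strategy, and the default keeps scores obtained on a treatment outside the estimand's own definition. On assumed use of 5% to 15% and extra relief of 1 to 2 points, an arm mean moves by 0.05 to 0.30 points. The true rate and relief are unknown, and the shift may be negligible.

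Two stronger readings are tempting. One is that VX-548 will be credited with other drugs' relief to an extent that undermines the primary result. The documents give no rate to support that, and significance at the planned change of 3 would survive the whole assumed range. The other is that affected scores should be deleted in the primary analysis. The check does not show that this is less biased. What is supported is a clearer estimand, a consistent responder rule and a sensitivity analysis.

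**What to change.** 1. **SAP 9.3.2.** For the NPRS responder and PGIC endpoints, count as a non-responder any subject taking a prohibited analgesic in the Week 12 window. Define this as Table 9-2 pain treatments other than acetaminophen and stable aspirin. Limit it to use while the restriction applies, because the PGIC window in Appendix A runs to Day 92, past the Week 12 target of Day 85.
2. **SAP 9.3.1.1.** Name prohibited analgesic use as an intercurrent event. Keep the all-scores rule as primary, under an explicit treatment policy strategy, and word the treatment attribute to match.
3. **Sensitivity analysis.** Prespecify an MMRM for NPRS and DSIS that sets scores to missing during use plus an analysis washout fixed before unblinding. State a rule for partial medication dates. Appendix C moves a missing start day to the first of the month and a wholly missing start to before first dose, which could delete weeks that preceded actual use.

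**Cost.** SAP wording, a changed responder flag and one extra model run for each of the two scales. Indication and start and stop dates are already collected (protocol 9.5). Responder rates may fall slightly, and the sensitivity analysis loses a little precision. Its missing-at-random assumption can overstate benefit if switching follows current lack of relief, so it should be read beside the primary analysis and not in place of it.
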